United States, with a disproportionate burden faced by Latinos. Small businesses pose a particular risk. They are more likely to employ low-wage Latino workers, and often use hazardous solvents containing volatile organic chemicals that can cause asthma, cancer, cardiovascular, and neurological disease; yet their workers lack access to culturally and linguistically appropriate occupational health and pollution prevention information due to economic, physical, and social barriers. CHW-led interventions and outreach in Latino communities have documented increased access to health care and health education and reduced workplace exposures among farmworkers. CHWs are an innovative method to bridge the gap between these small business communities and other stakeholders. The proposed project will capitalize on established partnerships between the University of Arizona, the Sonora Environmental Research Institute, Inc. and the El Rio Community Health Center. A community-engaged research framework will be used to complete three specific aims: 1) Quantify and identify exposures to hazardous chemicals in the two high risk small business sectors common in our target area (i.e., auto repair shops and beauty salons); 2) Work collaboratively with business owners, trade groups, workers and CHWs to design an industrial hygiene-enhanced CHW intervention tailored for each small business sector; and 3) Conduct a cluster randomized trial to evaluate the effectiveness of the CHW intervention at reducing workplace exposures to volatile organic compounds and assess which factors led to successful utilization of exposure control strategies in both male and female-dominated businesses. Businesses will be randomized to either an intervention or delayed intervention group, both of which will receive incentives to participate, such as worksite health screenings. CHWs will work closely with business owners and employees to select and implement exposure-strategies appropriate for their worksite using a menu of complementary strategies of varying complexity and cost. This innovative project has the potential to directly reduce occupational health disparities through a CHW intervention that moves beyond providing occupational health education. The intervention will overcome current barriers by helping marginalized Latino workers and small business owners who may have limited education, literacy, and computer skills to understand the hazards associated with their work, and will empower them to have greater control over their occupational exposures, with the ultimate goal of preventing occupational disease and reducing health disparities.

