
## **2) Purpose**

**Project Goal:** Determine if an industrial hygiene-enhanced community health worker (CHW) intervention can significantly reduce workplace exposures to hazardous chemicals in small businesses that mainly employ marginalized minority workers.

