## 7) Recruitment Methods and Consenting Process

### a. Recruitment Process:

Businesses will be recruited with the assistance of SERI CHWs and the Tucson Hispanic Chamber of Commerce. The project will be described to the business owner/manager and if they agree to participate and sign the site authorization form, workers will be told about the project's overall goals of community health interventions leading to decreased exposure to potentially dangerous chemicals in their workplace. In Aim 1, we are recruiting 20 businesses so that we can obtain an idea of current baseline VOC exposure levels and work practices, as well as owner/manager and worker ideas about health and safety in the workplace via interviews and focus groups. These are small businesses and SERI CHWs typically go door-to-door and explain the project orally. In Aim 3, we will recruit 120 businesses using the same methods as developed in Aim 1.

In Aim 3, once the business owner/manager agrees for their business to participate and signs the site authorization, the owner/manager will be recruited into the study, allowing the study team to get information about their shop and work practices critical for choosing effective ways of reducing chemical exposures (see *Owner\_Consent* document).

Once the business owner/manager is recruited, individual employees and the owner/manager (if they do similar activities as workers) will be recruited with the goal of measuring four full-shift exposures per business (see *AirSampling\_Consent* document). In Aim 3, we will complete four full-shift exposures in three different visit periods for a total of 12 full-shift exposures per business.

If the small business does not have four workers that are willing to participate, multiple measurements may be taken on the same workers on multiple days. Employees and owner/managers will also be recruited to join focus groups and do interviews, respectively. However, since the shops participating in Aim 1 are not able to participate in the randomized control trial in Aim 3 (for statistical reasons), we will only work with businesses with enough potential participants to consent to complete monitoring for 4 work shifts for any part of Aim 1.

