Work Should Not Hurt You: Reduction of Hazardous Exposures in Small Businesses
Through a Community Health Worker Intervention

ClinicalTrials.gov ID NCT03455530

PI: [name] (University of Arizona)

Statisticians: [name] supervised by [name] (University of Arizona)

January 16, 2024

Statistical Analysis Plan

Descriptive statistics will be calculated for shop and participant characteristics. Differences in baseline characteristics between the immediate and delayed intervention groups will be tested using the Welch Two-Sample t-test for continuous variables and Fisher's Exact Test for categorical variables. For all analyses, all tests will be two-sided, with a p-value < 0.05 considered statistically significant.

To analyze the primary outcome TVOC data, we will use linear mixed models to account for the lack of independence from repeated measurements within a shop at an assessment and across assessments. We will use contrasts to test the change in TVOC concentration from pre- to post-intervention between the arms. To account for possible confounding, we will fit both unadjusted and adjusted models. The unadjusted model has log-transformed TVOC concentration as the outcome, with fixed effects for intervention group (immediate, delayed), assessment time (1, 2, 3), and their two-way interactions; random effects will be included for shop and assessment time within shop, with random intercepts to account for correlations of shifts within the same shop and the potentially stronger correlations of shifts within the same shop at the same assessment. Random effects are assumed to be independent. Models for auto and beauty shops will be run separately because of differences in potential covariates for adjusted models.

Covariates for the adjusted models are selected based on their logical relevance and potential impact on exposures. For auto shops, additional covariates will be outside ventilation (i.e., working outside) and average shift apparent temperature. For beauty shops, additional covariates will be baseline air exchange rate and whether the shop offered nail services. The main results will be obtained from the adjusted models, because they provide a more accurate representation by accounting for relevant covariates.

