To explore the impact of different model choices, additional adjusted model results will be provided in the Supplemental Material. Specifically, covariates that change the treatment effect by more than 10% when added one-at-a-time as a main effect to the unadjusted model for each sector will be included. The following shift-level covariates at each assessment will be considered: apparent air temperature and self-report activity and ventilation data. The following shop-level covariates at each assessment will also be considered: apparent air temperature; outside TVOC concentration; if the building was rented or owned; if an owner or manager wore a monitor during that shop assessment; self-report activity and ventilation data aggregated to the shop-level; if it was a home business; number of people working that day; number of rooms in shop; if the shop uses "green" products; shop volume (calculated from measured shop dimensions); ventilation data (same categories as those for self-report plus wall heater, personal heater, central heater,

and extractor); and for beauty shops only, air exchange rate and whether the beauty shop provided nail services in addition to hair.

To analyze the secondary outcome of hazard scores derived from specific VOC data, we will use similar mixed models as described above to test the change in hazard score from pre- to post-intervention between the arms (although there will not be a random effect for shift within a shop assessment, because shift-level data are not taken for this outcome). Data preparation, cleaning, and statistical analyses will be performed using R version 4.4.1, the tidyverse package for data wrangling, the lme4 package for linear mixed effects models, and other packages listed in the Supplemental Material.

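### The main auto-shop model adjusts for working outside without fixing it at baseline, so the headline result may not be the total effect of the intervention

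*SAP*

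**What the plan says.** The third paragraph of the SAP lists the covariates of the adjusted models. For one sector: "For auto shops, additional covariates will be outside ventilation (i.e., working outside) and average shift apparent temperature". For the other: "For beauty shops, additional covariates will be baseline air exchange rate and whether the shop offered nail services". The beauty-shop air exchange rate is tied to baseline; the auto-shop outside-work variable has no stated timing or level.

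The reason for adjusting is in the second paragraph: "To account for possible confounding, we will fit both unadjusted and adjusted models". The third paragraph then ranks the two: "The main results will be obtained from the adjusted models", on the ground that adjustment represents the data more accurately.

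The fourth paragraph, on supplemental models, shows how ventilation is otherwise handled: "The following shift-level covariates at each assessment will be considered: apparent air temperature and self-report activity and ventilation data". It also lists self-reported ventilation aggregated to shop level and further shop-level ventilation data, again for each assessment.

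The protocol (Section 3, item 2, Purpose) sets the goal as finding out whether the intervention "can significantly reduce workplace exposures to hazardous chemicals in small businesses". Item 1 (Background) says that businesses are randomised and that CHWs help each one choose and put in place exposure controls "using a menu of complementary strategies of varying complexity and cost". Item 7a (Recruitment Process) says owners are enrolled first, "allowing the study team to get information about their shop and work practices critical for choosing effective ways of reducing chemical exposures".

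**The concern.** In a randomised comparison of change, the arms' difference in log TVOC estimates the total effect of assignment, by whatever route it arises. Adjusting for a variable recorded after randomisation keeps that meaning only if assignment does not affect the variable. Where work is done could be affected: CHWs collect work-practice information in order to choose controls, and moving solvent work outdoors is a plausible control.

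If it is affected, the adjusted contrast compares shifts with the same work location. It drops the benefit that came from moving work outside. It also becomes open to unmeasured causes shared by work location and TVOC, such as the kind of job done on that shift, because randomisation does not balance these within levels of a post-randomisation variable. Confounding is therefore not a reason to include it: randomisation already deals with confounding of the total effect, and chance differences in shift conditions are part of the sampling error.

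At stake is the headline answer for one of the two sectors. If the two planned models disagree, the SAP directs readers to the one further from the trial's question, and they could not tell how much of the gap is effect acting through outside work.

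**Working it through.** **1. Is the covariate a current value?** The text does not settle it. Three features point that way:

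- The beauty-shop air exchange rate carries a baseline label and the auto-shop variable does not. The supplemental list includes air exchange rate at each assessment, so the SAP does distinguish baseline from current values.
- Its companion in the auto-shop model, temperature, is a shift average.
- Every ventilation measure in the supplemental list, shift-level or shop-level, is taken at each assessment.

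**2. Closed form.** The documents contain no effect size, variance or power calculation, so there is no plan figure to reproduce. Let d be the rise in the proportion of shifts worked outside caused by the intervention, r the ratio of TVOC outside to inside, and b the effect on log TVOC with location held fixed. With no interaction and no unmeasured common cause:

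- total effect = b + d × ln(r)
- a model conditioning on current location returns b
- share removed = d × ln(r) / [b + d × ln(r)]

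All values of d, r and b are assumptions.

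| d | r | b | d × ln(r) | Total | Share removed |
|---|---|---|---|---|---|
| 0 | any | any | 0 | b | 0% |
| 0.10 | 0.6 | −0.7 | −0.051 | −0.751 | 6.8% |
| 0.20 | 0.5 | −0.2 | −0.139 | −0.339 | 41% |
| 0.30 | 0.4 | −0.2 | −0.275 | −0.475 | 57.9% |

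Alternatively, fix the total TVOC ratio at 0.70 (log −0.357). With r = 0.5, the ratio targeted by the current-location model is exp(−0.357 − d × ln 0.5): 0.70, 0.75, 0.80 and 0.86 for d = 0, 0.10, 0.20 and 0.30.

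**3. Simulation of the SAP model.** From the documents: 60 auto shops (protocol, Section 3, items 3 and 4), three assessments of four shifts (item 7a), group-by-time fixed effects, and random intercepts for shop and assessment within shop (SAP, second paragraph). Assumed:

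- 30 shops per arm; immediate arm treated before assessment 2, delayed arm before assessment 3
- variances 0.3 (shop), 0.1 (assessment within shop) and 0.4 (residual)
- 30% of shifts outside before intervention, with a between-shop SD of 0.1

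The contrast is the between-arm difference in change from assessment 1 to 2, with 500 replicates per scenario.

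| Scenario | Unadjusted | Current-shift adjusted |
|---|---|---|
| A. No change in outside work, b = −0.2 | −0.195 | −0.196 |
| B. d = 0.20, r = 0.5, b = −0.2 | −0.341 (rejects 51%) | −0.199 (rejects 24%) |
| C. As B, self-report sensitivity and specificity 0.8 | −0.340 | −0.295 |
| D. As B, common cause raises outside work and lowers TVOC | −0.337 | −0.129 |
| E. As B, strong common cause raises both | −0.353 | −0.377 |

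In B the apparent reduction falls from 1 − exp(−0.341) = 29% to 1 − exp(−0.199) = 18%. The share removed is (0.341 − 0.199)/0.341 = 42%, in line with the closed form. In C it is (0.340 − 0.295)/0.340 = 13%.

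**4. The baseline version.** Adding each shop's assessment-1 share of outside shifts gave the same estimate as the unadjusted model to three decimals in every scenario. This is expected: in complete, balanced data a shop-constant main effect carries no information about within-shop change.

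**5. Price of the fix.** Current-shift location explains some within-shop variance. Without it the standard error is 3% to 10% wider across the assumed scenarios, for example 0.173 against 0.163, and 0.173/0.163 = 1.06.

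**The case against.** Neither condition is stated in the documents. The control menu is not included, and nothing says that CHWs relocate work. Nail services also lack a baseline label, yet are plainly a shop characteristic, so a missing label proves little. Temperature is explicitly a shift average and working outside is not. The unadjusted model is fully specified and will be fitted, so no analysis is missing. With only 60 shops per sector, and possibly different workers at each assessment, adjusting for shift conditions can gain precision. Every effect and variance input above is assumed, and imperfect self-report shrinks the gap.

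Much of this stands. The exact level of the covariate is open, the mechanism is plausible rather than shown, and neither size nor direction follows from the documents. It does not remove the point. All the ventilation data in the supplemental list are collected at each assessment, so even a shop-level value could be post-randomisation. The unadjusted model is planned, but the SAP ranks it below the adjusted one for accuracy. A precision gain does not justify conditioning the headline estimate on something the intervention may change.

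**Conclusion.** The concern holds in conditional form. It is certain that the covariate's timing and level are undefined in the model chosen for the main auto-shop result. A current, post-randomisation value is the natural reading but remains an inference. If it is correct and the intervention changes where work is done, the headline contrast is not the total effect. The assumed scenarios run from no loss at all to 58% of the log-scale effect, 13% to 42% in the middle case depending on how well outside work is reported, and bias in either direction when unmeasured common causes are present. If outside work does not respond to the intervention, the only consequence is a small gain in precision. This is an inexpensive improvement in covariate definition and choice of headline model, held with medium confidence. It does not undermine the trial.

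**What to change.** - State when and at what level working outside is recorded.
- In the main auto-shop model, use its assessment-1 value (for example, the shop's share of baseline shifts worked outside) or leave it out. Apart from the temperature term, and with complete balanced data, this gives the contrast of the unadjusted model already planned. In effect, the change is to which model leads.
- If current-shift outside work is kept, report that model beside the unadjusted result as a sensitivity or mediation analysis.
- Label supplemental models containing post-intervention ventilation, activity, green-product use or air exchange as explanatory. The rule of keeping covariates that move the treatment effect by more than 10% can select variables that carry the effect. This last change is editorial.

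The cost is SAP wording and the choice of headline model, with no new data. The downside is a standard error about 3% to 10% wider than with current-shift location, under the assumed inputs.

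### The 10% change-in-effect screen for the supplemental models admits post-intervention variables that the intervention plausibly changes, and so biases those supplemental estimates toward zero

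*SAP*

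**What the plan says.** The SAP paragraph on additional adjusted models gives their purpose: "To explore the impact of different model choices, additional adjusted model results will be provided in the Supplemental Material". The selection rule, applied in each sector, is to include "covariates that change the treatment effect by more than 10% when added one-at-a-time as a main effect to the unadjusted model".

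Two candidate lists follow, and both are tied to each assessment:
- **Shift level:** "The following shift-level covariates at each assessment will be considered: apparent air temperature and self-report activity and ventilation data".
- **Shop level:** the list opens with "The following shop-level covariates at each assessment will also be considered". It includes "self-report activity and ventilation data aggregated to the shop-level", green-product use, ventilation categories with an extractor among them and, for beauty shops, air exchange rate. It also holds traits that hardly change within a shop: rented or owned, home business, number of rooms and volume.

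Neither list is limited to values from before the intervention. The main adjusted model for beauty shops, by contrast, uses baseline air exchange rate.

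On what the intervention does, the protocol (Section 3, 1) Background) says that community health workers help owners and employees to "select and implement exposure-strategies appropriate for their worksite using a menu of complementary strategies". The items on that menu are not given.

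**The concern.** In a randomised comparison, a covariate moves the treatment estimate for one of two reasons: chance imbalance between the arms, or a change in the covariate caused by treatment. A change-in-estimate screen cannot tell these apart. The more of the effect a variable carries, the more surely it passes, yet a variable on the pathway should not be adjusted for when the question is whether the intervention lowers exposure.

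Here the candidates include what an intervention against airborne VOCs would be expected to alter: how the shop is ventilated, how work is done and which products are used. If the intervention works through these, the supplemental models will show a smaller effect than the main models. A reader could conclude that the result depends on modelling choices, when the shrinkage only shows how the intervention worked.

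**Working it through.** The documents give no effect size, variance or power figure for this point, so there is no stated figure to reproduce.

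**Inputs from the documents.** 60 shops per sector (Protocol, Setting of the Human Research); four shifts in each of three visit periods (Protocol, Recruitment Process); log TVOC with arm, assessment and their interaction, and random intercepts for shop and for assessment within shop (SAP).

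**Assumptions.** 30 shops per arm; delayed arm treated after assessment 2, so the effect is the arm difference in change from assessment 1 to 2; balanced data; log-scale variances of 0.6 (shop), 0.3 (assessment within shop) and 0.6 (shift).

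**Step 1, precision.** The shop intercept cancels in the within-shop change. The variance of the contrast is 2 × 2 × (0.3 + 0.6/4)/30 = 4 × 0.45/30 = 0.06, so the SE is 0.245.

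**Step 2, what adjustment removes.** A 30% reduction is ln(0.7) = −0.357 on the log scale. Suppose use of a control rises from 30% to 70% in treated shops and carries half the effect.
- Coefficient of the control: 0.5 × (−0.357)/0.40 = −0.446.
- Expected adjusted effect: −0.357 − (−0.446 × 0.40) = −0.178.
- As a reduction: 1 − exp(−0.178) = 16%.

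In general, a control carrying a share m of the effect moves the estimate on average by that share. So its average shift exceeds the 10% threshold whenever m is above 10%.

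**Step 3, how often it is selected.** In simulation (1,500 trials per scenario, variances as above, 30% reduction), the control is selected in 79%, 96% and 99% of trials when it carries a quarter, a half and three quarters of the effect. With half carried, simulated estimates fell from a reduction of about 30% to 31% to one of about 16% to 18%.

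**Step 4, other variances.** Log-SDs for shop/assessment/shift of 1.0/0.6/0.8, 1.0/0.9/0.8 and 0.8/0.4/0.6 give SEs of 0.26, 0.36 and 0.18. Uptake here was taken as 50% of shops, from a 30% baseline. Ranges are over the three sets.

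| True reduction | Control carrying 25% | Carrying 50% | Carrying 100% | Prognostic, unaffected by treatment |
|---|---|---|---|---|
| 10% | 73–78% selected | 76–84% | 87–95% | 68–82% |
| 30% | 76–83% | 93% to over 99% | over 99% | 58–62% |
| 50% | 85–96% | over 99% | 100% | 37–41% |

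At a 50% reduction (log effect about −0.69), adjustment gives about −0.52, −0.34 and 0.00 for the three shares. Only the carried share is lost. A control that the intervention raises but that does not affect TVOC leaves the average estimate unchanged.

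**Step 5, noise.** A pure-noise covariate varying by assessment passes in 31–35% of trials with no effect, 11–22% at a 30% reduction and 1–10% at a 50% reduction. With ten such covariates offered and all that pass included (variances of Step 1):
- With no effect, the mean estimate stays at 0.00 and rejection goes from 5.0% to 5.4%.
- At a 30% reduction, the mean log effect goes from −0.357 to −0.354 and rejection from 30.3% to 30.6%.

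**Step 6, fixed shop traits.** The contrast is a difference in within-shop change, so a trait constant within a shop cancels when entered as a main effect. In balanced data the contrast moved by no more than 5e-15, and such traits were selected in 0% of trials. The screen therefore acts almost entirely on time-varying candidates, among which the likely pathway variables sit.

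**The case against.** The strongest reply is that nothing important rests on these models. The main results come from adjusted models with named covariates, an unadjusted model is also fitted, and the rule-selected models are supplemental and described as exploring model choice. A reader can set all three side by side. This stands, and it limits the point to the supplemental estimates and how they are read.

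Four stronger readings are tempting, and none is supported:
- **The supplemental models remove the effect.** They remove the share carried by the selected controls. The loss is total only if those controls carry everything, and the documents give no such share.
- **Selecting noise gives a wrong answer.** It makes the covariate set arbitrary, but Step 5 shows almost no change in the mean estimate or the rejection rate.
- **The documents name these variables as intervention targets.** They do not. For ventilation, activity, products and air exchange this is a reasonable inference from the protocol's Background. For outside TVOC it is weak.
- **The screen always favours pathway variables strongly.** At a 10% reduction the preference over ordinary prognostic covariates is slight (73–95% against 68–82%). It is clear at a 50% reduction (85–100% against 37–41%).

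It is also fair to say that restricting the set to baseline values would be an empty check if they were entered only as main effects, by Step 6. The fix has to deal with that.

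**Conclusion.** The point holds for the supplemental models. Applied exactly as written, the rule tends to select post-intervention variables that carry part of the effect, and adjusting for them pulls the estimate toward zero by that part. With half of a 30% reduction carried, selection is near certain (about 96%) and the reported effect roughly halves on the log scale, to a reduction of about 16% to 18%.

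The direction held under every variance set tried. The size rests on assumed variances, uptake, carried share, equal allocation, timing of the delayed arm and balanced data, none of which the documents supply. It also rests on the inference that the intervention alters ventilation, activity, product use or air exchange.

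A reader might infer that the trial's main conclusion is compromised. This rule gives no ground for that, because the main models do not use it. The change is worth making because these models are the plan's stated look at model choice, and their shrinkage is open to misreading.

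**What to change.** 1. Remove current-assessment ventilation (including extractor), activity, green-product use and air exchange rate from the 10% screen. Report models containing them separately, labelled as mechanism (mediation) analyses.
2. For the model-choice check, replace the screen with a covariate set named in advance:
   - time-varying covariates that the intervention does not plausibly change, such as apparent temperature, number of people working that day, and whether an owner or manager wore a monitor;
   - baseline values of ventilation, product use and air exchange rate, together with the fixed shop traits, each entered with an interaction with assessment time, since as main effects they cannot move the contrast in balanced data.
3. Do not add assessment-1 TVOC as a covariate. It is already an outcome in this model, which includes assessments 1, 2 and 3.

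The cost is SAP wording, with the same data and software. The downsides are small: a few more parameters, and less time-varying adjustment in the supplemental models.
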